Contact DAIDS through the RSC Safety Office at [contact] or call [name] or [contact]; or [contact] or [contact].

Telephone Calls

Sites are responsible for documenting telephone calls made to A5395 team members.

- Send an e-mail message to [contact].

Protocol-Specific Web Page

Additional information about management of the protocol can be found on the protocol-specific web page (PSWP).

GLOSSARY OF PROTOCOL-SPECIFIC TERMS

AE	adverse event
ARDS	acute respiratory distress syndrome
Azithro	azithromycin
CFR	Code of Federal Regulations
CI	confidence interval
CLIA	Clinical Laboratory Improvement Amendments
COPD	chronic obstructive pulmonary disease
COVID-19	Coronavirus Disease 2019
CQMP	Clinical Quality Management Plan
CrCl	creatinine clearance
CVD	cardiovascular disease
DHHS	Department of Health and Human Services
DMID	Division of Microbiology and Infectious Diseases
DRESS	drug reaction with eosinophilia and systemic symptoms
DSMB	Data and Safety Monitoring Board
EC	Ethics Committee
eCRF	electronic Case Report Form
FDA	Food and Drug Administration
EKG	electrocardiogram
GCP	Good Clinical Practice
GI	gastrointestinal
HCQ	hydroxychloroquine
HTN	hypertension
IB	Investigator Brochure
ICF	informed consent form
ICU	intensive care unit
IND	Investigational New Drug Application
IRB	Institutional Review Board
IV	intravenous
MERS	Middle East Respiratory Syndrome
NIAID	National Institute of Allergy and Infectious Diseases
NIH	National Institutes of Health
OHRP	Office for Human Research Protections

PHI	Protected Health Information
PI	Principal Investigator
SAE	serious adverse event
SAP	Statistical Analysis Plan
SARS-CoV-2	Severe Acute Respiratory Syndrome coronavirus 2
SDCC	Statistical and Data Coordinating Center
SOP	Standard Operating Procedure
SUSAR	Suspected Unexpected Serious Adverse Reaction
TdP	torsades de pointes
WHO	World Health Organization

SCHEMA

A5395

A Randomized, Double-blind, Placebo-controlled Trial to Evaluate the Efficacy of Hydroxychloroquine and Azithromycin to Prevent Hospitalization or Death in Persons with COVID-19

DESIGN

This is a phase IIB, double-blind, placebo-controlled, randomized trial, designed to compare the efficacy of hydroxychloroquine (HCQ) plus azithromycin (Azithro) versus placebo to prevent hospitalization and death in symptomatic adult outpatients with COVID-19 **caused by SARS-CoV-2 infection.**

DURATION

24 weeks. Treatment will be for 7 days with 23 weeks of follow-up.

SAMPLE SIZE

2000 participants who start study treatment; approximately 1000 participants in each of two treatment arms (A and B). Participants who are randomized but do not start study treatment will be replaced. A subset (200 participants who start treatment) will follow an additional sampling evaluation schedule.

POPULATION

Symptomatic, outpatient, adults (≥ 18 years) with SARS-CoV-2 infection

STRATIFICATION

Stratification will be by “high” versus “low” risk of progression to severe COVID-19, where “high risk” is defined as a person age ≥ 60 years or having at least one of several specified comorbidities.

REGIMEN

Participants will be randomized 1:1 to receive active/placebo study treatment as follows: HCQ/Placebo **400 mg orally twice a day on Day 0** followed by 200 mg **orally twice a day for 6 days**, and Azithro/Placebo 500 mg **once on Day 0**, followed by 250 mg daily for **4 days**.

1.0 HYPOTHESIS AND STUDY OBJECTIVES

1.1 Hypothesis

1.1.1 Hydroxychloroquine (HCQ) and Azithromycin (Azithro) will prevent hospitalization and death in persons with symptomatic SARS-CoV-2 infection.

1.2 Primary Objective

1.2.1 To determine if HCQ and Azithro will prevent the composite endpoint of either hospitalization or death by 21 days after study entry. Hospitalization is defined as ≥ 24 hours of acute care.

1.3 Secondary Objectives

1.3.1 To determine safety of HCQ and Azithro including 1) adverse events (AEs) leading to early discontinuation of treatment with HCQ and Azithro and 2) cardiac AEs.

1.3.2 To determine if HCQ and Azithro reduce the frequency of detection and levels of SARS-CoV-2 RNA in site-collected nasopharyngeal (NP) swabs and self-collected nasal swabs in subset of participants.

1.3.3 To determine if HCQ and Azithro change the severity and duration of self-reported symptom experience of COVID-19.

1.3.4 To determine if HCQ and Azithro will prevent the composite endpoint of either hospitalization or death by 24 weeks after study entry. Hospitalization is defined as ≥ 24 hours of acute care.

1.4 Exploratory Objectives

1.4.1 To explore if outpatient HCQ and Azithro change the hospital course once a participant requires hospitalization.

1.4.2 To identify pretreatment hematology, chemistry, and inflammatory biomarkers that are associated with outcomes.

1.4.3 To explore differences in outcomes between HCQ and Azithro versus placebo treatment groups among subgroups of the population, notably by sex, race/ethnicity, and risk groups defined by age and comorbidities.

1.4.4 To explore possible predictors of outcomes across the study population, notably sex, race/ethnicity, and risk groups defined by age and comorbidities.

- 1.4.5 To determine the comparability between site-collected NP swabs and self-collected nasal swabs for the detection of SARS-CoV-2 shedding.

2.0 INTRODUCTION

2.1 Background

Threat

A novel pneumonia caused by a previously unknown betacoronavirus emerged in Wuhan, China, in December 2019. The virus is closely related to the severe acute respiratory syndrome coronavirus (SARS-CoV-1), which led to an outbreak in 2003, and has been named SARS-CoV-2. The human disease caused by SARS-CoV-2 is called COVID-19.

During the current SARS-CoV-2 outbreak, the incidence of known cases has rapidly increased such that, on January 5, 2020, there were 59 confirmed cases, 278 cases on January 20, 2118 cases on January 26, and more than 80,000 cases and 2700 deaths as of February 25, 2020, according to various international health reporting agencies. As a result, on January 30, 2020, the International Health Regulations Emergency Committee of the World Health Organization (WHO) declared the COVID-19 outbreak a Public Health Emergency of International Concern. On January 31, 2020, the US Department of Health and Human Services declared a public health emergency in the United States. As of **April 22, 2020**, there are **2,594,724** cases of COVID-19, including **826,248** cases in the United States (US), resulting in a total of **179,778** deaths globally. Despite quarantine measures, SARS-CoV-2 continues to spread [1]. Outbreak forecasting and modeling suggest that these numbers will continue to rise [2].

Global efforts to evaluate novel antivirals and therapeutic interventions to treat COVID-19 have intensified. There is currently no vaccine to prevent SARS-CoV-2 infection or therapeutic agent to treat COVID-19. Therefore, there is an urgent public health need for rapid development of novel interventions.

[figure not shown]
Virology

Coronaviruses (CoVs) are positive-sense, single-stranded, enveloped RNA viruses, many of which are commonly found in humans and cause mild symptoms. Over the past two decades, emerging pathogenic CoVs capable of causing life-threatening disease in humans and animals have been identified, namely, SARS-CoV-1 in 2002-2003 and Middle East Respiratory Syndrome coronavirus (MERS-CoV) in 2012.

Disease Course

Once infection occurs, the clinical course is variable. Best current data suggest that fewer than 2.5% of infected persons will show symptoms within “2.2 days (CI, 1.8 to 2.9 days) of exposure, and symptom onset will occur within 11.5 days (CI, 8.2 to 15.6 days) for 97.5% of infected persons” [3]. In most (~80%) cases, COVID-19 presents as a mild-to-moderately severe, self-limited acute respiratory illness with fever, cough, and shortness of breath. It remains unclear exactly what the rate of progression of COVID-19 is and what the predictors are for complications, including pneumonia, acute respiratory

distress syndrome (ARDS), kidney failure, and death. It is clear that older age, male sex, and comorbidities including diabetes and hypertension increase the risk for worse outcomes (Figure 2.1-1) [4-6]. In a recent meta-analysis, the main clinical symptoms were fever (88.5%), cough (68.6%), myalgia or fatigue (35.8%), expectoration (28.2%), and dyspnea (21.9%). Minor symptoms included headache or dizziness (12.1%), diarrhea (4.8%), and nausea and vomiting (3.9%) [7]. Laboratory examinations showed that lymphocytopenia (64.5%), increase of C-reactive protein (CRP) (44.3%), increase of lactate dehydrogenase (LDH) (28.3%), and leukocytopenia (29.4%) were more common in those with COVID-19 [4, 8].

Shedding

Viral infections jump from host to host through a variety of pathways. CoVs do this through respiratory droplets. Understanding this shedding is important to understanding epidemic spread and how shedding relates to disease progression. Best evidence available now suggests that viral shedding, especially in upper respiratory secretions, is detectable around 2 days before symptoms develop and continues throughout the symptomatic phase. This shedding can be quite high during active disease and can continue for up to 37 days, with a quarter of persons still shedding at 3 weeks, as detected by nasopharyngeal swabs [4].

Biomarkers

The literature also points to a systemic inflammatory response that predicts disease progression and death. Having a biomarker panel that can predict such progression early would be helpful in making clinical decisions and triaging clinical care [4]. In particular, patients requiring ICU admission had higher blood levels of interleukin (IL)2,

IL7, IL10, granulocyte colony stimulating factor (GCSF), interferon gamma-induced protein (IP)10, monocyte chemoattractant protein 1 (MCP1), macrophage inflammatory protein 1-alpha (MIP1A), and tumor necrosis factor-alpha (TNF α) than hospitalized patients not requiring ICU admission [5]. Nothing is currently known about which inflammatory biomarkers during early infection might predict increased risk for hospitalization.

Biomedical Interventions

There are no approved treatments for COVID-19. Some agents have shown activity against other betacoronaviruses, such as lopinavir/ritonavir, chlorpromazine, nitazoxanide, gemcitabine, and dasatinib [9], and two agents have shown *in vitro* activity against the virus, including chloroquine and the adenosine analog remdesivir [10]. There is no clinically proven antiviral treatment for SARS-CoV-2 infection, although a clinical trial of remdesivir [11] is underway in China [12], and the US for severe pulmonary disease, and anecdotal evidence has been published about HCQ and Azithro [13].

Chloroquine and its less toxic derivative HCQ (first FDA approved in 1955 for the treatment of malaria) have garnered substantial interest as off-label treatment for COVID-19. They are alkalinizing lysosomotropic drugs that accumulate in lysosomes [14]. Both drugs block viral infection by increasing endosomal pH, which is required for viral particles to fuse with a cell. Chloroquine also interferes with glycosylation of cellular receptors of CoV, including SARS-CoV [15]. *In vitro* data in Vero E6 cells have demonstrated that chloroquine functions at both entry and at post-entry stages of the SARS-CoV-2 infection, unlike remdesivir [10]. Further *in vitro* data showed that there is an exposure-response relationship for HCQ (Figure 2.1-2). Both drugs also modulate the immune response, and have long been used to treat autoimmune diseases such as rheumatoid arthritis, porphyria cutanea tarda, and lupus [14]. Such immune modulation may also help in thwarting ARDS [16].

HCQ Pharmacology

HCQ and chloroquine have similar pharmacokinetics, with rapid gastrointestinal absorption and elimination by the kidneys. Both are also metabolized by the cytochrome P450 enzymes (CYP2D6, 2C8, 3A4, and 3A5). HCQ is metabolized to desethylhydroxy-chloroquine, desethylchloroquine, and bidesethylhydroxychloroquine by the liver and excreted by the kidneys, with desethylhydroxychloroquine being most common [17, 18a]. The absorption half-life is 3 to 4 hours and the terminal half-life ranges from 40 to 50 days. Based on modeling of HCQ pharmacokinetics and its antiviral effects, [name] at UCSF found that higher doses of HCQ would be associated with progressive loss of detection

[figure not shown]
[figure not shown]

Figure 2.1-2: *In vitro* Activity of Remdesivir, Hydroxychloroquine, and Chloroquine [10]

of SARS-CoV-2 in the nasopharynx over 6 days of dosing (**Figure 2.1-3**), in a dose-dependent manner [18b]. However, higher doses are also associated with longer QT interval prolongations; thus, **in order to balance the potential risks and benefits for treatment in the outpatient setting**, treatment in this trial will include a loading dose of **800 mg divided into two 400 mg doses taken 12 hours apart starting at enrollment**, followed by 200 mg twice daily for 6 days (12 doses), with a total dose of 3200 mg of HCQ during the study.

HCQ Interactions

HCQ does not have significant interactions with most other medications, but may enhance liver toxicity of select drugs, for example, aurothioglucose, cimetidine, or digoxin. It can also increase the blood plasma concentrations of penicillamine, which may contribute to the development of side effects from penicillamine, and decrease the levels of ampicillin and praziquantel. It can also enhance hypoglycemic effects of insulin and oral hypoglycemic agents.

Azithro Pharmacology

Azithro was first approved for clinical use in 1988 [19]. It is currently FDA approved for use in mild to moderate bacterial infections including sinusitis, community acquired pneumonia, urethritis/cervicitis, pharyngitis, and acute bacterial exacerbations of chronic obstructive pulmonary disease. It is the first of the azalide class of antimicrobials, which does not undergo significant metabolism and does not complex with or induce cytochromes P450 (CYPs), therefore decreasing the potential for drug interactions [19, 20]. Azithro has been found to have a long terminal half-life of 50 hours with 500 mg IV dosing and 79 hours with 500 mg oral dosing, making once a day or single dose treatments possible [21]. It is also known to have a large volume of distribution and achieves extensive tissue penetration compared to macrolides [20], **as well as** high

intracellular concentrations in immune cells [22]. The co-administration of meals along with Azithro has no impact on bioavailability [23].

Azithro Interactions

In pre-clinical studies, Azithro has been shown to increase QT intervals, but without inducing torsades de pointes (TdP) [24]. Given QT prolongation may occur, concurrent Azithro administration is not recommended with high-risk QT-prolonging agents, such as fexinidazole and pimozide. Other QT-prolonging agents such as antipsychotics or class IC antiarrhythmics should be used with caution with monitoring of QT_c interval. In addition, Azithro as a P-glycoprotein (P-gp) inhibitor should be avoided in concurrent use of colchicine, topotecan, rimegepant, pazopanib, or vincristine, as it may increase the serum concentration of these drugs [25]. There is conflicting evidence on the effect of Azithro on warfarin drug metabolism. In general, it appears that there is a modest decrease in warfarin clearance and thus a possible increase in anticoagulant effect [26]. Patients should continue to have international normalized ratio monitored when Azithro is used with warfarin. In addition, there is potential risk of increased rhabdomyolysis with concurrent use of statins, and patients should be monitored on such therapy [27].

HCQ and Azithro Interactions

There are no pharmacologic drug-drug interactions between Azithro and chloroquine, and thus none are expected between Azithro and HCQ, including in pregnant women [28, 29].

Potential Risks of HCQ and Azithro

HCQ and Azithro have each been used widely for many years, for the independent indications described previously. Potential risks are described further in this section below.

HCQ

Common side effects of HCQ include headache, emesis, diarrhea, vision changes, and muscle weakness. Severe side effects are mainly limited to allergic reactions and eye toxicity, "chloroquine retinopathy" [30], and cardiac toxicity. "Chloroquine retinopathy" is a relatively serious toxicity associated with HCQ use among people taking HCQ for greater than 5 years [31]. Further, rapid-onset retinopathy has been reported in persons being treated with erlotinib and high-dose HCQ (1000 mg daily) for non-small cell lung cancer [32]. Generally, people taking **400** mg of HCQ or less per day or for short periods have a negligible risk of retinopathy, as macular toxicity is related to total cumulative dose [22]. The dose and durations proposed in this trial are unlikely to cause retinopathy [31].

HCQ can prolong the QT interval, and ventricular arrhythmias and TdP have been reported, but usually after prolonged administration [33], particularly in patients with lupus and other comorbidities such as end-stage renal disease [34-37]. **In general**, drug-induced TdP and life-threatening ventricular arrhythmias from HCQ are very rare and typically only observed when doses of 5 g or more are taken [14, 33, 38]. HCQ is a derivative of chloroquine, and the relationship between chloroquine and QT prolongation has been better defined. It is the same molecule that is associated with a prolonged QTc

interval. When chloroquine was administered to healthy adults (regimen 600 mg + 600 mg + 300 mg on Days 1, 2, and 3, respectively) the average increase in QTc interval was 28 ms (18-38 ms; 95% CI) with no cardiac AEs reported [39]. While chloroquine and HCQ are different compounds, animal toxicity studies indicate HCQ is two to three times less toxic across different species [40].

Further, the WHO states, “[d]rug-induced TdP and life-threatening ventricular tachyarrhythmias are very rare events, and there are no simple screening tests to identify people at risk.” Also from WHO, “[d]espite hundreds of millions of doses administered in the treatment of malaria, there have been no reports of sudden unexplained death associated with quinine, chloroquine or amodiaquine, although each drug causes QT/QTc interval prolongation” [38].

Azithro

Common side effects associated with both oral and IV administration of Azithro include nausea and vomiting, likely due to increased gastric motility [19]. Severe side effects include pseudomembranous colitis, exacerbation of myasthenia gravis, Stevens-Johnson syndrome/toxic epidermal necrolysis, and drug reaction with eosinophilia and systemic symptoms (DRESS) [41, 42]. In addition, there is an increased rate of cancer relapse for hematopoietic stem cell transplant patients with acute lymphocytic leukemia (ALL), acute myelocytic leukemia or bronchiolitis obliterans who received long-term Azithro therapy (greater than 2 years) [43]. However, patients taking Azithro for short periods have a negligible risk of this complication. Azithro crosses the placenta and is found in low concentrations in breast milk, but is considered safe to use in pregnancy [44].

Prolongation of QT with Azithro treatment has been seen in pre-clinical studies, but clinical studies of long term treatment with Azithro have not observed this effect [45]. Additionally, in the preclinical studies that demonstrated QT prolongation with Azithro, the QT prolongation did not lead to TdP, the clinical outcome of concern [24]. Furthermore, in clinical studies of long-term treatment (median of 9 months) with Azithro in patients with non-tuberculous mycobacterial infection, no significant change in QTc intervals and no cardiovascular events were observed during the treatment period [45].

COVID-19

There are some concerning reports that COVID-19 is associated with cardiac disease. In particular, a recent study in China found that persons with underlying cardiovascular disease are at high risk for severe disease and death [46]. It is unclear if cardiac morbidity is worse in the setting of COVID-19 **with** other pneumonia-causing pathogens [47], and unknown if the risks of short course HCQ and Azithro differ in the context of COVID-19.

Assessment of Potential Risks and Benefits

Although there are limited clinical data of HCQ plus Azithro use, there are preclinical data on using chloroquine plus Azithro in a rapid-pacing model in an anesthetized guinea pig model, which has been shown to be predictive of concentration-dependent onset of TdP [48]. This study evaluated increasing doses of azithromycin dehydrate and chloroquine diphosphate given intravenously that achieved clinical use concentrations.

The investigators reported no biologically significant effect on mean alternans. In fact, when combined, Azithro reduced the magnitude of alternans observed with chloroquine alone. This preclinical data is supported by clinical studies using chloroquine with Azithro. The Kimani et al. study evaluated malaria prevention during pregnancy where 1445 women received 3 days of chloroquine plus Azithro that was repeated at 4-8 week intervals during the second and third trimesters of pregnancy. Although QT intervals were not assessed at baseline or throughout the study, there were no reported cardiac AEs [29]. Sagara et al. conducted two randomized, comparative, non-inferiority studies in Africa where patients with malaria received Azithro 1000 mg (n=227) or Azithro 500 mg (n=9) with chloroquine 600 mg, all once daily for 3 days [49]. While QT interval was not measured at the beginning or during the study, there were no cardiac AEs noted. While subjective adverse events of dizziness and palpitations were reported, they occurred no more frequently than seen in the mefloquine control arm. **The azithromycin label reports that, in comparison to chloroquine alone, the maximum mean (95% upper confidence bound) increases in QTcF are 5 (10) ms, 7 (12) ms, and 9 (14) ms, with the co-administration of 500 mg, 1000 mg, and 1500 mg azithromycin, respectively.**

Given that the proposed study will exclude those taking **concomitant** medications with high risk of prolonging QT ([section 5.4.1](#)), we do not feel that electrocardiograms (EKGs) at study entry or during treatment are needed. **We believe that** exclusions on the basis of baseline QTc are unlikely to add significantly to **overall safety, above and beyond the planned exclusion** of participants with higher risk for drug-induced ventricular arrhythmias and cardiac events **based upon** relevant personal or family cardiac history, high risk clinical history including severe renal and liver disease, and those who are taking additional QTc prolonging agents. Further, in the midst of a global pandemic, the risk-benefit assessment must consider a wide range of participants, study staff and resource utilization-related issues. In this case, the condition of TdP is expected to be very rare and the performance of EKGs would require the use of personal protective equipment (PPE), for which supplies must be carefully preserved as the current pandemic escalates, and the risk of additional direct contact between staff and highly infectious study participants. As a result, we feel that the potential benefit of HCQ plus Azithro treatment for a disease with an overall case fatality rate of up to 3% (and based on preliminary estimates in the US, 3-11% among persons aged 65-84 years) outweighs the very small risk of a treatment-related cardiac AE, and therefore do not feel that EKGs at study screening or during treatment would be justified [50, 51].

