4.2 Exclusion Criteria

(Medical history can be by self-report. Refer to the A5395 MOPS.)

- 4.2.1 Need for hospitalization or immediate medical attention in the clinical opinion of the study investigator.
- 4.2.2 History of or current hospitalization for COVID-19.

NOTE: Individuals hospitalized and then discharged, even if only hospitalized for 1 day, are excluded.

4.2.3 History of ventricular arrhythmia or **using antiarrhythmics within the past 30 days**.

4.2.4 Personal or family history of Long QT syndrome.

4.2.5 History of kidney disease.

NOTE A: If the individual responds “yes” but can provide a creatinine clearance (**CrCl**) value **of** ≥ 45 mL/min by Cockcroft-Gault equation **from** within 1 year **of** study entry, the individual may participate.

NOTE B: Please refer to the A5395 PSWP for the website link to the Cockcroft-Gault calculator.

4.2.6 History of ischemic or structural heart disease.

4.2.7 History of hypokalemia or hypomagnesemia or taking potassium supplementation or magnesium supplementation.

4.2.8 Personal medical history of porphyria, retinopathy, severe hepatic impairment, or G6PD deficiency.

4.2.9 Use of drugs with possible anti-SARS-CoV-2 activity within 30 days prior to study entry, e.g., remdesivir, lopinavir/ritonavir fixed dose combination, ribavirin, chloroquine, hydroxychloroquine, and azithromycin, or participation in a clinical trial involving any of these drugs whether for treatment or prophylaxis.

4.2.10 Requirement or expected requirement for a medication that significantly prolongs QT intervals or increases risk for QT prolongation (medications summarized in [section 5.4](#)), from 96 hours prior to study entry through 4 weeks after discontinuation of study treatment **except for escitalopram, citalopram, maprotiline, SC/IM risperidone, carbamazepine, ethosuximine, and zonisamide, which should not be used within 7 days prior to study entry.**

4.2.11 Loop diuretics are exceptions to exclusion criterion 4.2.10 but these cannot be used within 30 days prior to study entry.

4.2.12 Participating in a study where co-enrollment is not allowed.

4.2.13 Receipt of a SARS-CoV-2 vaccination prior to study entry.

4.2.14 Known allergy/sensitivity or any hypersensitivity to components of HCQ, azithromycin, or their formulation.

4.2.15 Active drug or alcohol use or dependence that, in the opinion of the site investigator, would interfere with adherence to study requirements

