5.4 Concomitant Medications

Whenever a concomitant medication or study agent is initiated or a dose changed, investigators must review the concomitant medication's and study agent's most recent package insert, Investigator's Brochure, or updated information from DAIDS to obtain the most current information on drug interactions, contraindications, and precautions.

Additional drug information may be found on the ACTG Precautionary and Prohibited Medications Database located at http://tprc.pharm.buffalo.edu/home/di_search/.

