5.4.1 Prohibited Medications

- Non-study HCQ and Azithro
- Cardiac medications
 - Antiarrhythmic drugs: Class Ia (quinidine, procainamide, disopyramide); Class III (dofetilide, ibutilide, sotalol)
 - **Loop diuretics (furosemide, bumetanide, torsemide, ethacrynic acid)**
- Non-cardiac medications
 - Diphenhydramine
 - **Antiepileptic medications (carbamazepine, eslicarbazepine, ethosuximide, felbamate, gabapentin, lamotrigine, levetiracetam, oxcabazepine, phenobarbital, phenytoin, piracetam, pregabalin, Rufinamide, stiripentol, tiagabine, topiramate, sodium valproate, valproic acid, zonisamide)**
 - Antipsychotic and antidepressant agents: Neuroleptic (haloperidol, droperidol, thioridazine, chlorpromazine); Atypical antipsychotics (ziprasidone, risperidone, zimeldine, citalopram); Antidepressants (amitriptyline, desipramine, imipramine, maprotiline, doxepin, fluoxetine, escitalopram, citalopram)
 - Antibiotics: quinolone (levofloxacin, moxifloxacin); Macrolide (erythromycin, clarithromycin)
 - Antimalarials (quinine, halofantrine, **chloroquine**)
 - Antiprotozoal (pentamidine)
 - Antifungal (azole group)
 - Antimotility Agents
 - Methadone

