5.4.2 Precautionary Medications

A list of precautionary medications can be generated using the ACTG Precautionary and Prohibited Medications Database located at http://tprc.pharm.buffalo.edu/home/di_search/

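### Section 2.1 says azithromycin should be avoided with five named P-gp drugs, but the protocol's prohibited list, exclusion criteria and concomitant-drug stopping rule do not act on that advice

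*Protocol*

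**What the plan says.** The part of Protocol section 2.1 on azithromycin interactions says that the drug "should be avoided in concurrent use of colchicine, topotecan, rimegepant, pazopanib, or vincristine". The reason given is a possible rise in the serum concentration of those drugs through P-gp inhibition. It is not a QT reason.

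The operative sections read as follows.

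- **5.4.1 Prohibited Medications** opens with "Non-study HCQ and Azithro". It then names antiarrhythmics, loop diuretics, antiepileptics, antipsychotics and antidepressants, certain antibiotics, antimalarials and other agents, many of them individually, for example "Neuroleptic (haloperidol, droperidol, thioridazine, chlorpromazine" and "Antiprotozoal (pentamidine".
- **5.4.2 Precautionary Medications** prints no list. It says "A list of precautionary medications can be generated using the ACTG Precautionary and Prohibited Medications Database".
- **5.4 Concomitant Medications** sets a general duty: "Whenever a concomitant medication or study agent is initiated or a dose changed, investigators must review" current interaction information on both products. It adds "Additional drug information may be found on the ACTG Precautionary and Prohibited Medications Database".
- **4.2.10** excludes a "Requirement or expected requirement for a medication that significantly prolongs QT intervals or increases risk for QT prolongation" and refers to 5.4 for the drugs meant.
- **9.1** lists a need for a prohibited concomitant medication, by reference to 5.4, among the reasons to end treatment permanently.

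**The concern.** The protocol gives avoidance advice about five named drugs in its background section and then sets no rule for them where sites look for rules. A site that applies 4.2, 5.4.1 and 9.1 as printed could enrol and dose someone who takes one of these drugs, and could continue treatment if one is started. Whether that happens would depend on each investigator's reading of package inserts.

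The situation is foreseeable. Section 3.0 gives cancer therapies as an example of the medication-related immunocompromise that places a person in the high-risk stratum, and 10.3 aims for at least half of enrolment in that stratum. Topotecan, pazopanib and vincristine would ordinarily be cancer treatment. Because the trial is double-blind, the investigator will not normally know who receives azithromycin, so a fixed rule applied to both arms suits the design better than judgement case by case.

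What is at stake is participant safety and internal consistency. The sample size, the endpoint and the type I error are not involved.

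**Working it through.** No figure in the plan needs to be reproduced. The check sets the advice in 2.1 beside each section that could give it effect.

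| Where a rule could sit | What is there | Any of the five drugs? |
|---|---|---|
| 4.2, criteria 4.2.1 to 4.2.15 | Drug-related criteria cover antiarrhythmics, potassium or magnesium supplements, drugs with possible anti-SARS-CoV-2 activity, QT-risk drugs and loop diuretics | 0 of 15 criteria cover them as P-gp drugs |
| 5.4.1 | Printed prohibited list | 0 of 5 named, and no P-gp class entry |
| 5.4.2 | Pointer to an outside database | None printed |
| 5.4 | Duty to review package inserts, the Investigator's Brochure or sponsor updates | None named, and no action prescribed |
| 9.1 | One ground tied to a concomitant drug: a prohibited medication under 5.4 | Not reached through the printed list |

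Taking these in order:

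1. **Entry.** The broadest drug criterion, 4.2.10, is confined to QT risk and points to 5.4 for its drugs. The advice in 2.1 rests on raised serum levels, so that criterion does not capture it. Criterion 4.2.9 concerns possible antiviral activity, and none of the five is among its examples.
2. **Day 0.** Starting the study agent triggers the review in 5.4. The information needed is at hand: 6.3.5 collects all prescription drugs from the last 7 days and a complete cancer chemotherapy history, at screening with an update at entry. The review does not say whether the person is to be excluded, dosed or held.
3. **During treatment.** If one of the five is started, the 5.4 review applies again. The concomitant-drug ground in 9.1 applies only if the drug counts as prohibited, and the only prohibited list printed under 5.4 is 5.4.1.

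A person taking, say, colchicine or vincristine could therefore meet every printed criterion, be dosed, and have no printed concomitant-drug ground for stopping.

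Pimozide and fexinidazole, which 2.1 says are not recommended with azithromycin, are also absent from 5.4.1. Their position differs. The reason for them is QT risk, so 4.2.10 already covers them at entry, including expected use until 4 weeks after treatment ends. Only an unforeseen start during treatment is left open.

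**The case against.** The strongest reply is that the protocol works in tiers. The printed prohibited list is largely about QT risk, which is the safety concern that section 2 develops at length. Other interactions are left to the mandatory review in 5.4 and to the outside database. Section 2.1 also mentions warfarin and statins, which are not prohibited either. Azithromycin is given for only five days (Day 0 plus four). Section 9.1 cites 5.4 as a whole, and the database's title covers prohibited as well as precautionary drugs, so it may list these five. The manual of procedures may too.

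Much of this stands. There is a real interaction check, its input is collected, and the sources not shown may close the gap in practice. It does not remove the mismatch. For warfarin and statins, 2.1 asks for monitoring, whereas for these five it says avoid. The review in 5.4 prescribes no exclusion, hold or stop. Within 5.4 the database is offered as additional information and, in 5.4.2, as the source of precautionary drugs. A precautionary listing would not trigger 9.1.

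A reader might infer more than the text supports, in four ways.

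- *That 9.1 ends treatment only for prohibited drugs.* It also does so for drug-related toxicity, a possibly related serious adverse event, participant request, life-threatening clinical reasons and, in the sampling subset, low Day 0 creatinine clearance. Sections 8.2 and 8.3 add investigator discretion for toxicity. The limitation holds only for grounds tied to a concomitant drug.
- *That use after entry would go unrecorded*, because rimegepant fits no category in 6.3.6 and colchicine fits none clearly. The diary in 6.3.10 asks participants to log the medications they take on Days 0 to 20, with staff review, so a separate recording fix is largely redundant.
- *That the lack of study blood tests outside the subset makes this worse.* Even in the subset, the only laboratory result with a stopping rule is Day 0 creatinine clearance.
- *That pimozide and fexinidazole are uncontrolled.* Criterion 4.2.10 deals with them at entry.

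**Conclusion.** The point holds as a minor participant-safety misalignment. The protocol advises against combining azithromycin with five named drugs, and its prohibited list, exclusion criteria and concomitant-drug stopping ground do not carry that advice into a rule. Power, the primary endpoint and the primary analysis are unaffected.

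The size in participants cannot be given. The documents contain no figure for use of these drugs; it is probably small, and any count would be guesswork.

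The conclusion rests on two things: reading the avoidance statement in 2.1 as meant for this trial's participants, and judging the protocol on its printed text, without the outside database or the manual of procedures. If either source prohibits the five drugs, what remains is to bring the printed protocol into line with it. The documents do not support a reading that participants are without any interaction safeguard.

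**What to change.** 1. Add colchicine, topotecan, rimegepant, pazopanib and vincristine by name to 5.4.1, so that the concomitant-drug ground in 9.1 applies.
2. Add one exclusion criterion to 4.2: current use, or expected use during study treatment, of any of the five.
3. Optionally, name pimozide and fexinidazole in 5.4.1 for tidiness.

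The cost is five names in one list (seven with the optional pair), one criterion and a screening-checklist update. No new entry data are needed, because 6.3.5 already collects the drug history. The downside is a few more screen failures, some of them high-risk participants on cancer therapy, whom the trial wants to enrol. A participant who has to start one of these drugs would also stop study treatment in either arm, including on placebo.

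If the sponsor considers a five-day azithromycin course acceptable with these drugs, the alternative is to say so: revise the advice in 2.1 and state in 5.4 how users are to be managed.
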